10.2 Effectiveness Assessments

Effectiveness will be assessed as Clariscan vs all GBCAs together and Clariscan vs individual GBCA. The assessment will be done in 2 stages:

Stage 1: by the local radiologist and nurse/technician

Stage 2: by a panel of 3 MR experts, blinded to the use of GBCAs independently for the first 50 images transferred to GEHC. The first 25 images of Clariscan and first 25 images all other GBCAs will be used for the analysis as 1:1 ratio. This analysis will be performed at a later date and not part of the initial read out of the study.

Stage 1

Three parameters will be assessed for effectiveness of GBCAs, including Clariscan, by local radiology (A & B) and technician/nurse (C) as first stage of assessment:

- A- Image quality reported by the local radiologist.
- B- Diagnostic confidence reported by the local radiologist.
- C- Customer satisfaction survey reported by the local nurse/radiology technician recorded once per centre during the study for each GBCA used at the study centre, including generics.

A- Image quality reported by the local radiologist

Quality of image will be assessed by the local reporting radiologist on a 4-point Likert scale.

This is based on literature review for the assessment of CE-MR images. The definition for cardiovascular MRA and MRI images are on a 4-point Likert scale and defined in following section.

MRA: [[Hansmann et al. 2014](#)]: For the qualitative assessment, blinded readers assessed image quality on a scale of 1 to 4:

- 1 = poor image quality and blurring of the arterial segment
- 2 = fair image quality, inadequate arterial enhancement for confident diagnosis
- 3 = good image quality and arterial enhancement, adequate for confident diagnosis
- 4 = excellent image quality and arterial enhancement, for highly confident diagnosis

MRI: [[Maravilla et al. 2017](#)] used the following definition for overall visualisation and characterisation of the lesion (or most representative lesion, i.e., enhancing and/or largest if there was >1 lesion present) were assessed on a 4-point scale:

- 0 = poor, inadequate
- 1 = fair, partial
- 2 = good, adequate
- 3 = excellent

Based on the literature review in this study, image quality will be captured on the following 4-point scale:

	MRI	MRA
1	poor, inadequate;	poor image quality and blurring of the arterial segment;
2	fair, partial	fair image quality, inadequate arterial enhancement for confident diagnosis
3	good, adequate;	good image quality and arterial enhancement, adequate for confident diagnosis;
4	excellent	excellent image quality and arterial enhancement, for highly confident diagnosis)

The results will be reported as comparison of Clariscan to all GBCAs and Clariscan vs individual GBCA if the cohort is bigger than 100 cases.

B- Diagnostic confidence reported by the local radiologist

For each patient based on the **most representative lesion**. All available sequences (e.g., fluid attenuation inversion recovery [FLAIR], T2, and T1 with and without contrast administration) will be available for readers to review and evaluate. **Before reviewing the CE-MR image**, the radiologist will be asked to enter the confidence to make a diagnosis for the patient as a whole number between 0% to 100% based only on the non-enhanced image. The radiologist will then enter the diagnostic confidence as a whole number between 0% to 100% after the CE-MR scan results are read. This will be used to calculate the change in diagnostic confidence in this study by the local radiologist for all GBCAs including Clariscan. The results will be reported as comparison of Clariscan to all GBCAs and Clariscan vs individual GBCA if the cohort is bigger than 100 cases.

C- Customer satisfaction survey reported by the local nurse/radiology technician recorded once per centre during the study for each GBCA used at the study centre, including generics

Reported once per centre by MR nurse/technician from the investigator's staff - Quality of packaging including bottles, syringe, marking, pack size available. This will be recorded once for each GBCA used at the study centre as an overall impression and rated as:

[figure not shown]
1 = can be improved

2 = good

3 = excellent

The results will be reported as comparison of Clariscan to all GBCAs and Clariscan vs individual GBCA.

Figure 3 Effectiveness Assessments

Stage 2 (to be performed at a later date): assessment by a panel of 3 MR experts, blinded to the use of GBCAs independently for the first 50 images transferred to GEHC. The first consecutive 25 images of Clariscan and first consecutive 25 images all other GBCAs will be used for the analysis as 1:1 ratio.

A subgroup of patients will be selected to transfer the anonymised images to GEHC through AGMednet. The images will be archived at GEHC to be analysed at a later date by an expert MR radiologist panel to assess the quality of images. The first 50 images will be transferred in 1:1 ratio for Clariscan and other GBCAs, i.e., the first consecutive 25 images for Clariscan and the first consecutive 25 images of the other GBCAs (excluding liver-specific GBCAs). In total, a maximum of 850 patients' images will be transferred from all study centres. If sufficient number of images (25) for Clariscan or other GBCA group are not acquired in 3 months, the recruitment will stop at 3 months and all images for either group will be transferred for blinded read.

- Collective anonymised and blinded images for all GBCAs including Clariscan from all centres will be assessed and analysed by a panel of 3 MR expert radiologists. There will be no centre-level analysis or comparison for Clariscan and other GBCAs.
- Quality of images reported by 3 MR expert radiologists blinded to the GBCAs use and inter-observer variability.
- Correlation between local radiologist rating and blinded radiologist rating.

This analysis will not be part of the initial read out of the study and will be performed at a later date.

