5 STUDY OBJECTIVES AND PURPOSE

The GBCA observational study, will prospectively collect data on the pattern of use for GBCA in real-life diagnostic settings with special reference to Clariscan after its commercial launch in Europe.

The primary and secondary objectives of the study are as follows:

5.1 Primary Objective:

To understand the pattern of use of GBCAs in MRI centres in Europe.

5.2 Secondary Objective:

To assess the effectiveness and safety profile of GBCAs, including Clariscan, in real-life settings.

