6.2 Study Rationale

GBCAs are essential to enhanced the images in MR examinations. Over the course of time GBCAs have faced challenges and controversies. It is essential to understand how clinicians use GBCAs in clinical practice including the referral pattern, why enhance, how to select a contract agents, what attributes are important for clinicians in the decision-making process and understanding the process and practice in the real world.

The primary objective of the GBCA observational study, will be to prospectively collect data on the pattern of use for GBCA in real-life setting with special reference to Clariscan after its commercial launch in Europe. The data will be collected for CE-MR procedure and patients in detail to understand the clinical practice. To completely understand the overall picture of radiology practice in an institution the collective data of all radiological procedures by the investigator and the institution will be collected for the recruitment period. This will help understand what proportion of CE-MR procedures are performed by the investigator and institution.

A qualitative analysis will be performed describing the referral pattern and challenges in a radiological practice.

In addition, as a secondary objective, the study will look at the effectiveness reported as quality of images, diagnostic confidence and customer satisfaction reported on a Likert scale by the local radiologist/technician and spontaneously reported immediate and delayed AEs to assess the effectiveness and safety profile of GBCAs in clinical practice respectively.

During the study, the images will be collected and archived for the initial 50 cases from each investigation centre to be analysed separately at a later stage by a panel of 3 expert MR radiologists. The images will be assessed for the quality of images on the same scale as assessed by the local radiologist. The aim of this second, separate statistical analysis will be to assess the quality of images and see the inter-observer agreement by the expert MR radiologist and assess the agreement in quality of images between real-world reporting by the local radiologist and MR experts' assessment. This analysis will not be part of initial read out of the study due to lack of funding and will be performed at a later date. The current study will be an opportunity to collect and archive the images.

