12.2 Populations for Analysis

Full Analysis Set

The Full Analysis Set will include all enrolled patients who signed the informed consent.

Effectiveness Analysis Set

The Effectiveness Analysis Set will include all patients who received a GBCA and underwent an MR examination.

Safety Analysis Set

The Safety Analysis Set will consist of all patients who received GBCA during the study.

Investigator Analysis Set

The Investigator Analysis Set will include all investigators who performed at least one GBCA-enhanced MR procedure as part of this study.

Centre Analysis Set

The Centre Analysis Set will include all centres that were approved and initiated to take part in this study and performed at least one GBCA-enhanced MR procedure as part of this study.

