12.6 Effectiveness Variables and Analyses

Effectiveness data will be summarised for all GBCAs pooled, for non-Clariscan GBCAs pooled, and for all individual GBCAs administered during the study, including Clariscan. Statistical differences in image quality and diagnostic confidence between groups (Clariscan vs non-Clariscan GBCAs pooled and Clariscan vs each individual GBCA) will be assessed at an alpha of 0.05. However, no formal statistical hypotheses will be tested and no adjustments will be made for multiplicity.

The following summaries will be provided for the Effectiveness Analysis Set:

- The average image quality.
- The average change in diagnostic confidence (diagnostic confidence using CE-MR enhanced image minus diagnostic confidence using the non-enhanced image).
- The proportion of patients for whom contrast-enhanced MRI changed the diagnosis (asked as a yes/no question on the eCRF).
- The proportion of patients for whom contrast-enhanced MRI increased the confidence in diagnosis (asked as a yes/no question on the eCRF).

Stage 2 analyses (Section 10.2) will be conducted at a later date and will be outlined in a separate analysis plan.

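### A nurse/technician rating of packaging is classed as one of three effectiveness measures, so a packaging comparison would be reported as effectiveness of Clariscan

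*Protocol*

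**What the plan says.** The secondary objective (protocol section 5.2) is "To assess the effectiveness and safety profile of GBCAs, including Clariscan, in real-life settings". Section 10.2 puts this into operation for Stage 1: "Three parameters will be assessed for effectiveness of GBCAs, including Clariscan". Parameters A and B are image quality and diagnostic confidence, both recorded by the local radiologist. Parameter C is a customer satisfaction survey completed by the local nurse or technician. The synopsis gives the same list of three, and section 6.2 repeats the classification: "effectiveness reported as quality of images, diagnostic confidence and customer satisfaction reported on a Likert scale".

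The only content stated for C is "Quality of packaging including bottles, syringe, marking, pack size available". On frequency, section 10.2 says "This will be recorded once for each GBCA used at the study centre as an overall impression", on a three-point scale. On reporting it says "The results will be reported as comparison of Clariscan to all GBCAs and Clariscan vs individual GBCA". For A and B the corresponding sentence goes on to require a cohort of more than 100 cases; for C no condition follows.

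Section 12.2 defines the analysis set for effectiveness by patients: "The Effectiveness Analysis Set will include all patients who received a GBCA and underwent an MR examination". Section 12.6 speaks of "Statistical differences in image quality and diagnostic confidence between groups", assessed at an alpha of 0.05. It then lists four summaries for that set: image quality, change in diagnostic confidence, change of diagnosis, and increased confidence in the diagnosis. Customer satisfaction is not among them.

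**The concern.** A rating of bottles, syringes, labelling and pack sizes carries no information on whether an agent enhances the image or helps the diagnosis. Because the protocol names it as an effectiveness parameter and promises a Clariscan comparison on it, following the plan would place a packaging score among the results that answer the secondary objective. A good score for the sponsor's product could then be read as evidence of effectiveness. A later analysis plan written to this protocol would inherit the label.

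There is also a question of comparability. Each rating comes from one centre's staff. If the ratings of one agent come from a different group of centres than the ratings of another, a difference in average score may reflect how readily those centres give high marks as well as the products themselves. With so few ratings and no minimum number, a comparison with an agent used at one or two centres could be reported alongside comparisons based on more than 100 patients.

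**Working it through.** The plan gives no sample size, power or error rate for this item, so there is no figure of its own to reproduce. The check is a comparison of sections, a count, and a short derivation.

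**1. Where item C appears and where it does not**

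| Place in the protocol | Treatment of item C |
|---|---|
| Synopsis, effectiveness assessments | Named as the third Stage 1 effectiveness parameter |
| Section 6.2 | Named as an effectiveness outcome |
| Section 10.2 | Named as effectiveness parameter C; content is packaging; comparison promised |
| Section 9.2 and Table 2 | Collected once, at completion of recruitment |
| Section 12.2 | Effectiveness Analysis Set consists of patients; a centre rating is not a unit in it |
| Section 12.6 | Neither summarised nor compared |

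So the assessment sections declare C an effectiveness measure with a comparison to be reported, while the analysis sections give it no summary and no analysis set. The two do not match.

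**2. Number of ratings**

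Input: centres by country in the synopsis, 2 + 3 + 3 + 3 + 1 + 1 + 1 = 14. With one rating per agent per centre, the maximum for any single agent, Clariscan included, is 14 × 1 = 14. Section 6.1 gives 17 centres; on that count the maximum is 17. An agent used at a single centre would have n = 1.

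**3. Minimum cohort**

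For A and B, comparisons with an individual agent require more than 100 cases. For C there is no minimum, although its largest possible n per agent is 14 (or 17).

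**4. Effect of pooling across centres**

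Write a rating as product effect + centre (rater) effect + error. Suppose all 14 centres rate Clariscan and k of them also rate agent X. The difference between the two simple averages then has expectation

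product difference + (mean centre effect over 14 centres − mean centre effect over the k centres)

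and the bracket equals

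[(14 − k)/14] × (mean centre effect of centres without X − mean centre effect of centres with X).

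- k = 14: the weight is 0/14 = 0. The centre effects cancel and the simple difference equals the within-centre one.
- k = 7 (chosen for illustration): the weight is 7/14 = 0.50.
- k = 1: the weight is 13/14 = 0.93.

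Taking the difference within each centre that rated both agents cancels the centre effect for every k, provided the rater effect is common to that centre's ratings. The size of the bracket cannot be given, because the protocol does not say which agents each centre uses or how far raters differ.

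**The case against.** The strongest reply is that nothing statistical in the effectiveness analysis changes. Section 12.6 confines the alpha 0.05 assessment to image quality and diagnostic confidence, the three parameters are not combined into a composite, and the study tests no formal hypothesis. The item is openly titled a satisfaction survey, and its packaging content is stated. All of this stands, and it limits the point to what is reported under the name of effectiveness. It does not remove it, because section 10.2 still promises the comparison under that name.

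A reader might go further in three ways that the protocol does not support:

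- **That centre ratings will be attached to patients**, so that a handful of ratings would look like thousands. Table 2 and section 9.2 collect the rating once at the end of recruitment, and nothing assigns it to patients or to the Effectiveness Analysis Set.
- **That the comparison will be made unpaired.** The protocol is silent on pairing, and an analysis plan could specify it. Where the same centres rate both products, ignoring the pairing leaves the average difference unchanged. The concern applies only where different centres contribute to different agents. Nor does the protocol say that one person rates every agent at a centre.
- **That the three-point scale is itself faulty.** Its lowest category is critical of the product, and no error follows from the choice of scale.

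**Conclusion.** The point holds as a matter of classification and reporting. The protocol makes packaging one of three effectiveness parameters, promises Clariscan comparisons on it with no minimum number of ratings, and gives it no place in the effectiveness analysis. The item rests on at most 14 Clariscan ratings on the synopsis count (17 on the count in section 6.1), and possibly on one rating for a rarely used comparator.

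The image quality and diagnostic confidence results are unaffected, and no error rate changes. What changes is which results may be called effectiveness. The warning about mixing rater and product differences is conditional: it assumes that agents are rated by different groups of centres, that those groups differ in how they score, and that the ratings are pooled without matching by centre. The protocol neither plans nor rules out such pooling.

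**What to change.** 1. In the synopsis and sections 6.2 and 10.2, take item C out of the effectiveness parameters and name it packaging satisfaction.
2. In section 12, add a descriptive summary of it on the Centre Analysis Set, by agent, with n stated as the number of ratings.
3. Compare Clariscan with another agent only among centres that rated both, as within-centre differences, and show the number of such centres with each comparison.
4. Limit effectiveness conclusions to image quality, diagnostic confidence and the related items already listed in section 12.6.

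The cost is wording only: no new data, patients or procedures. The sponsor loses one item from the effectiveness claim, and some comparisons with individual agents will rest on few centres.

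### Stage 2 aims at agreement between local and expert image ratings, but the synopsis and section 10.2 name correlation, which cannot show a systematic shift

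*Protocol*

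**What the plan says.** Protocol section 6.2 gives the purpose of the second, separate analysis. Apart from image quality itself, one aim is to "see the inter-observer agreement by the expert MR radiologist" and another is to "assess the agreement in quality of images between real-world reporting by the local radiologist and MR experts' assessment". It also fixes the scale: "The images will be assessed for the quality of images on the same scale as assessed by the local radiologist". Section 10.2 defines that scale for local readers: "image quality will be captured on the following 4-point scale", scored 1 to 4.

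The Stage 2 outputs listed in section 10.2 read differently. The first is "Quality of images reported by 3 MR expert radiologists blinded to the GBCAs use and inter-observer variability". The second is "Correlation between local radiologist rating and blinded radiologist rating". The synopsis (Effectiveness Assessments, Stage 2) repeats both. For the comparison of local and blinded ratings, neither place names a kappa, a percentage agreement, an absolute-agreement intraclass correlation (ICC) or a mean difference. Neither says how three expert scores become one blinded rating.

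Section 12.6 leaves the Stage 2 analyses to a separate analysis plan, which is not shown. Section 11.2 says the Stage 1 and Stage 2 data will be merged after the blinded read.

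**The concern.** Agreement asks whether two readers give an image the same score. Correlation asks only whether their scores rise and fall together, so a constant offset between readers leaves it unchanged. Because both sets of readers use the same 1-to-4 scale, agreement can be measured directly and nothing forces a retreat to correlation.

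The choice matters here because the local radiologist is not blinded (section 8.4), while local image quality scores are compared between Clariscan and other gadolinium-based contrast agents (GBCAs) at an alpha of 0.05 (section 12.6). The expert panel provides the only blinded assessment in the protocol. If local readers score more generously than blinded experts, in general or for one agent, the difference is a shift, and a correlation coefficient does not register a constant shift. A Stage 2 plan that followed the words of section 10.2 would therefore report a figure that does not answer the aim in section 6.2.

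**Working it through.** The protocol gives no coefficient, power or sample size for this comparison, so there is no figure to reproduce. The check is a constructed example on the protocol's own scale.

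**Inputs.** From the documents: scores 1 to 4, same scale for both readers (sections 6.2 and 10.2). Assumed: local scores of 2, 3 and 4 for 15%, 55% and 30% of images, and the shifts below. One expert rating per image is also assumed.

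**Local mean and variance.** Mean = 0.15×2 + 0.55×3 + 0.30×4 = 3.15. Variance = 0.15×4 + 0.55×9 + 0.30×16 − 3.15² = 10.35 − 9.9225 = 0.4275.

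**Case 1: every expert score is one point lower.**
- Expert = local − 1, so Pearson, Spearman and Kendall coefficients are all 1.00. Identical scores: 0%.
- Linear-weighted kappa = 1 − (observed mean |d|) / (chance-expected mean |d|). Observed = 1. Expected from the margins = 0.15×0.45 + 0.55×0.85 + 0.30×1.85 = 1.09. Kappa = 1 − 1/1.09 = 0.08.
- Quadratic-weighted kappa = 1 − (observed mean d²) / (sum of the two variances + squared mean difference) = 1 − 1/(0.4275 + 0.4275 + 1) = 1 − 1/1.855 = 0.46.
- Absolute-agreement ICC (large sample) = variance / (variance + shift²/2) = 0.4275 / (0.4275 + 0.5) = 0.46. A consistency-type ICC would be 1.00.

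**Case 2: a random 70% of images are one point lower.**
- Expert variance = 0.4275 + 0.7×0.3 = 0.6375. Correlation = √(0.4275/0.6375) = 0.82. Identical scores: 30%.
- Chance-expected mean |d| = 0.9655, so linear-weighted kappa = 1 − 0.7/0.9655 = 0.27 (0.275 to three decimals).

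**Case 3: the shift is confined to one agent.** Local readers score every Clariscan image one point above the experts and every other image the same; groups are of equal size with the same local distribution.
- Expert variance = 0.4275 + 0.5×0.5 = 0.6775. Pooled correlation = √(0.4275/0.6775) = 0.79.
- Mean local-minus-expert difference: 1.0 for Clariscan and 0 for the others.

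**Sensitivity of Case 1 to the assumed scores.** Other expert distributions on scores 1, 2 and 3 were tried: 283/283/284 and 85/255/510 (n = 850), 233/233/234 (n = 700) and 10/15/25 (n = 50). All gave correlations of 1.00 and 0% identical scores. Linear-weighted kappa ranged from 0.11 to 0.18, and quadratic-weighted kappa and absolute-agreement ICC from 0.47 to 0.57. The kappas and the ICC depend on the distribution; the pairing of 1.00 with 0% does not.

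**The case against.** The best defence is that the bullets in the synopsis and section 10.2 are topic labels. They name no coefficient, and the neighbouring phrase on inter-observer variability is just as informal. The only prose statement of purpose, in section 6.2, says agreement twice, and section 12.6 defers the methods. On this view the separate plan can still choose an agreement statistic, and an absolute-agreement ICC would satisfy both wordings. This stands in part. A reader might infer that the protocol has irrevocably fixed the wrong statistic; section 12.6 does not support that. The deferral does not remove the mismatch, however: the current text names a quantity that differs from its own aim, and an absolute-agreement ICC is mentioned nowhere.

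A reader might also infer that a high correlation would conceal overrating of every image and be taken to validate the local scores. That goes too far. The experts' image quality scores are themselves a listed output, and section 11.2 merges them with the local scores. A full-point gap in means could be seen. What is missing is a named paired comparison on the same images. The Stage 1 average in section 12.6 covers the whole Effectiveness Analysis Set, whereas Stage 2 covers "a maximum of 850 patients' images will be transferred from all study centres".

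Finally, a one-point shift applied to all images represents general leniency. It leaves the difference between Clariscan and other agents unchanged, so it does not demonstrate bias towards an agent. The documents give no evidence that either kind of shift will occur.

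Stage 2 is also secondary, outside the initial read-out and unable to alter locked Stage 1 data.

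**Conclusion.** The point holds as a mismatch between aim and named measure that should be corrected before the blinded read. Section 6.2 asks for agreement; the synopsis and section 10.2 name correlation; and on this 4-point scale correlation can be 1.00 when no image receives the same score from both readers. That extreme rests on an assumed uniform one-point shift. Under it, across the distributions tried, linear-weighted kappa is 0.08 to 0.18 and quadratic-weighted kappa 0.46 to 0.57. The cases show what correlation can miss and do not predict the data. No primary result is affected, and the images and ratings collected are the same whichever statistic is used.

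**What to change.** In the synopsis and section 10.2, replace correlation with agreement between local and blinded ratings, and carry the following into the separate Stage 2 plan:

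- A weighted kappa or an absolute-agreement ICC, with 95% CI. The kappa weights must be prespecified: in Case 1 linear weights give 0.08 and quadratic weights 0.46.
- Percentage exact agreement and mean local-minus-expert difference, on the same images.
- All of these pooled across centres, overall and separately for Clariscan and other GBCAs. This respects the exclusion of centre-level comparison in sections 7.1 and 10.2.
- A rule for forming the expert rating from three scores, for example the median, or each expert against the local reader.
- For agreement among the three experts, a multi-rater or pairwise agreement statistic. The local-minus-expert difference does not apply there.

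The cost is two lines of protocol wording plus the detail in a plan that has to be written anyway, with the same images and readers. The downside is that the reported figure may look less favourable than a correlation.
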